## 7.2. Part 2: Primary and Key Secondary Efficacy Objectives Estimands

The estimands corresponding to the Part 2 RWP primary and key secondary objectives and endpoints are described in Table 10 and Table 11, respectively.

**Table 10: Estimand for the Part 2 Primary Objective**

Objective	To evaluate efficacy of SYN1934v1 versus placebo in the responder population
A. Population	The population is the RWP responder full analysis set (defined in Section 8.2) characterized by the inclusion/exclusion criteria provided in Section 4.2.
B. Variable	Continuous variable: Change from RWP baseline to Week 4 in blood Phe level
C. Intercurrent events	
 
Treatment discontinuation: consistent with a treatment-policy strategy, treatment discontinuation will not be considered.
 
Antibiotic use: consistent with a treatment-policy strategy, antibiotic use will not be considered.
 
Prohibited medication use: consistent with a treatment-policy strategy, prohibited medication use will not be considered.
 

Objective	To evaluate efficacy of SYNB1934v1 versus placebo in the responder population
D. Population-level summary	The population-level summary is the least-squares means and difference in the change from baseline to Week 4 in blood Phe levels between the SYNB1934v1 and placebo treatment groups. An MMRM using an observed case approach is being applied. The post-baseline blood Phe levels at Weeks 1, 3, and 4 will be used. The MMRM model is described in Section 8.4.2.

MMRM = mixed model with repeated measures; Phe = phenylalanine; RWP = randomized withdrawal period.

**Table 11: Estimands for the Part 2 Key Secondary Objectives**

Objective	To evaluate the efficacy of SYNB1934v1 versus placebo in the responder population with regard to the proportion of participants with a blood Phe level $\leq 360$ $\mu\text{mol/L}$
A. Population	The population is the RWP responder full analysis set (defined in Section 8.2) characterized by the inclusion/exclusion criteria provided in Section 4.2.
B. Variable	Dichotomous variable: blood Phe level $\leq 360$ $\mu\text{mol/mL}$ at Week 4
C. Intercurrent events	
 
• Treatment discontinuation: consistent with a treatment-policy strategy, treatment discontinuation will not be considered.
 
• Antibiotic use: consistent with a treatment-policy strategy, antibiotic use will not be considered.
 
• Prohibited medication use: consistent with a treatment-policy strategy, prohibited medication use will not be considered.
 

D. Population-level summary	Difference in proportions between the SYNB1934v1 and placebo treatment groups. The analysis method is described in Section 8.5.
Objective	To evaluate the efficacy of SYNB1934v1 versus placebo in the responder population with regard to the change from DEP baseline in blood Phe level
A. Population	The population is the RWP responder full analysis set (defined in Section 8.2) characterized by the inclusion/exclusion criteria provided in Section 4.2.
B. Variable	Continuous variable: Change from DEP baseline to Week 4 in blood Phe level.
C. Intercurrent events	
 
• Treatment discontinuation: consistent with a treatment-policy strategy, treatment discontinuation will not be considered.
 
• Antibiotic use: consistent with a treatment-policy strategy, antibiotic use will not be considered.
 
• Prohibited medication use: consistent with a treatment-policy strategy, prohibited medication use will not be considered.
 

D. Population-level summary	The population-level summary is the least-squares means and difference in the change from DEP baseline to Week 4 in blood Phe levels between the SYNB1934v1 and placebo treatment groups. An MMRM using an observed case approach is being applied. The post-baseline blood Phe levels at Weeks 1, 3, and 4 will be used. The MMRM model is described in Section 8.5.
Objective	To evaluate the efficacy of SYNB1934v1 versus placebo in the responder population with regard to the percent change from DEP baseline in blood Phe level
A. Population	The population is the RWP responder full analysis set (defined in Section 8.2) characterized by the inclusion/exclusion criteria provided in Section 4.2.
B. Variable	Continuous variable: Percent change from DEP baseline to Week 4 in blood Phe level.

C. Intercurrent events	
 
• Treatment discontinuation: consistent with a treatment-policy strategy, treatment discontinuation will not be considered.
 
• Antibiotic use: consistent with a treatment-policy strategy, antibiotic use will not be considered.
 
• Prohibited medication use: consistent with a treatment-policy strategy, prohibited medication use will not be considered.
 

D. Population-level summary	The population-level summary is the least-squares means and difference in percent change from DEP baseline to Week 4 in blood Phe levels between the SYN1934v1 and placebo treatment groups. An MMRM using an observed case approach is being applied. The post-baseline blood Phe levels at Weeks 1, 3, and 4 will be used. The MMRM model is described in Section 8.5.

DEP = dose-escalating, open-label period; MMRM = mixed model with repeated measures; Phe = phenylalanine; RWP = randomized withdrawal period.

## 8. STATISTICAL METHODS AND DETERMINATION OF SAMPLE SIZE

### 8.1. General Statistical Methods

All evaluations and tabulations will be carried out as described in detail in a statistical analysis plan (SAP), which will be finalized and approved prior to the DEP interim analysis and database lock and unblinding.

A disposition of participants will be provided for each of the 3 parts of the study and will include a breakdown of participants who were randomized, treated, discontinued treatment, lost to follow-up, or withdrew consent (as appropriate).

Continuous variables will be summarized using the number of observations, mean, standard deviation (SD), median, minimum, and maximum. Categorical variables will be summarized using frequency counts and percentages.

Baseline for blood Phe level in each of the 3 parts of the study will be defined as the mean of the duplicate blood Phe level measurements obtained immediately prior to administration of the first dose of each part. If only one blood Phe level measurement is available, then that measure will be used as baseline. Similarly, for the determination of responders and participants who achieve a specific reduction in Phe (e.g., Phe level  $\leq 360$   $\mu\text{mol/L}$  at any time in the DEP, or a  $\geq 20\%$  reduction from baseline) the mean of the duplicate blood Phe level measurements at the applicable post-baseline timepoint (e.g., Week 3) will be used. If only one of the duplicate blood Phe levels is available at a particular post-baseline timepoint, then that measurement will be used. In describing the endpoints, the baseline and week numbering are specific to the corresponding study part, unless explicitly noted otherwise.

### 8.2. Populations for Analysis

Analysis populations will be defined for each of the 3 parts of the study (DEP, RWP, and OLE).

**Full analysis set (FAS):** The full analysis sets are based on the intention-to-treat principle. The DEP FAS includes all participants enrolled in the DEP.

The RWP FAS is defined as all participants randomized into the RWP. Additionally:

- The responder RWP FAS is defined as participants in the RWP FAS who are responders
- The nonresponder RWP FAS is defined as participants in the RWP FAS who are nonresponders

A responder is defined as a participant who achieves a  $\geq 20\%$  reduction in blood Phe level compared to DEP baseline on SYN1934v1 (i.e., this is an exploratory endpoint for the DEP, see [Table 1](#)).

The responder RWP FAS will be the primary efficacy analysis population for the RWP. Analyses on the RWP FAS will be performed according to the randomized treatment group.

In the event that, based on the interim analysis results utilizing the criteria provided in [Table 12](#), the DMC recommends dropping either the  $1 \times 10^{12}$  or the  $1 \times 10^{12}$  and  $6 \times 10^{11}$  doses, the DEP FAS will exclude all participants who were enrolled and treated at a dropped dose in the DEP. Additionally, the RWP FAS will exclude all participants who have been randomized in the RWP up to this time. The participants in the DEP who have an iTD corresponding to a dropped dose will go directly into the OLE part of the study (i.e., as opposed to being randomized into the RWP).

These participants who are excluded from the DEP FAS and RWP FAS will be summarized separately.

**Safety analysis set (SAS):** For each of the 3 study parts, the SAS will include all participants who received any amount of IMP in the corresponding study part with treatment assignment based on the treatment received.

**Per-protocol analysis set (PPS):** The DEP PPS is defined as all DEP FAS participants, who had no major protocol deviations that would affect efficacy, completed their final 3-week iTD, whose dietary Phe remained within 20% of their DEP baseline value, and who did not require systemic antibiotic treatment during DEP. The DEP PPS will be used as a sensitivity analysis for the DEP primary efficacy endpoint.

The responder RWP PPS is defined as all responder RWP FAS participants, who had no major protocol deviations that would affect efficacy, had at least 75% treatment compliance, whose dietary Phe remained within 20% of their DEP baseline value, and who did not require systemic antibiotic treatment during DEP or RWP (see [Section 4.3.4.2](#)). The responder RWP PPS will be used as a sensitivity analysis for the RWP primary efficacy endpoint. Major protocol deviations will be determined prior to the RWP database lock. Analyses on the responder RWP PPS will be performed according to the randomized treatment group.

### 8.3. Determination of Sample Size

[REDACTED]. This assumes a dropout rate of [REDACTED] and approximately 50% of participants are responders. If, during the course of the study, it becomes apparent that the assumptions were not accurate or a dose level is dropped after the interim analysis, the number of participants enrolled into the DEP may be adjusted. The study has over

[REDACTED]  
[REDACTED]  
[REDACTED]  
[REDACTED]. The mean percent reduction and standard deviation in blood Phe values used in the power calculations are based on results from a similar study in participants with PKU.

A sample size of [REDACTED]  
[REDACTED]  
[REDACTED]  
[REDACTED], a

[REDACTED] The power was calculated via a t-test. The mean treatment group difference and standard deviation in blood Phe values used in the power calculations are based on results from a similar study in participants with PKU.

## 8.4. Primary Efficacy Endpoint Analyses

The primary efficacy analyses for DEP and RWP are presented in the sections below. Sensitivity and supplemental analyses to support these analyses will be presented in the SAP.

### 8.4.1. Part 1: DEP

The DEP primary efficacy endpoint is the percent change from DEP baseline in blood Phe level at the last measurement of the iTD of SYNB1934v1. The last measurement is the participant's last Week 3 blood Phe level at the iTD of SYNB1934v1 (ie, as discussed in Section 3.2.1).

The mean percent change from baseline at the participant's iTD will be tested by an MMRM analysis. The MMRM model will have DEP baseline blood Phe level and iTD dose level as fixed effects. The dependent variable is the percent change from baseline in blood Phe level at the last measurement of the iTD of SYNB1934v1.

Least-squares means for the percent change from baseline overall and at each iTD dose level, along with the corresponding [REDACTED] and p-values testing a percent change from baseline equal to 0, will be calculated. The primary efficacy analysis will test the least-squares means percent change from baseline equal to 0 for the blood Phe level at the participants' last week (Week 3) at his or her established iTD.

At each of the scheduled assessments blood Phe will be drawn in duplicate. The MMRM will incorporate these participant repeated measures. For the MMRM analysis, the results of the post-baseline duplicate samples from the Week 3 visit will be included in the statistical model (i.e., without averaging the results within a given visit before inclusion into the MMRM).

The DEP FAS will be the primary efficacy analysis population.

### 8.4.2. Part 2: RWP

The RWP primary efficacy endpoint is the change from RWP baseline to Week 4 in blood Phe level. An MMRM analysis will be used to compare the mean change in blood Phe level between the placebo and SYNB1934v1 dose groups. The MMRM model will have treatment group, RWP

baseline blood Phe level, iTD dose level, visit, and visit  $\times$  treatment group (interaction effect), visit  $\times$  iTD dose level (interaction effect), and visit  $\times$  RWP baseline blood Phe level (interaction effect) as fixed effects. The MMRM will also incorporate the participant's repeated measures at visits Weeks 1, 3, and 4, with visit being treated as a categorical variable. Least-squares means for each treatment group and the SYN1934v1 treatment group difference from placebo, along with the corresponding [REDACTED] will be calculated for Weeks 1, 3, and 4. The primary efficacy analysis will compare the least-squares means treatment difference between SYN1934v1 and placebo in the change from baseline in the blood Phe level at Week 4.

At each of the scheduled assessments, blood Phe will be drawn in duplicate. The MMRM will incorporate these participant repeated measures. For the MMRM analysis, the results of each of the post-baseline duplicate samples from a visit will be included in the statistical model (i.e., without averaging the results within a given visit before inclusion into the MMRM).

The responder RWP FAS will be the primary efficacy analysis population.

## **8.5. Key Secondary Efficacy Endpoint Analyses**

### **8.5.1. Part 1: DEP**

The key secondary efficacy endpoints for the DEP are:

- Change from baseline in blood Phe level at last measurement of the iTD of SYN1934v1
- $A \geq 20\%$  reduction from baseline in blood Phe level at any time of the iTD of SYN1934v1
- $A \geq 20\%$  reduction from baseline in blood Phe level at any time in the DEP.

The key secondary endpoint, change from baseline in blood Phe level at last measurement of the iTD of SYN1934v1, will be analyzed using an MMRM analysis similar to the model described for the DEP primary efficacy analysis (Section 8.4), with the dependent variable being the change in blood Phe level from DEP baseline.

For the 2 key secondary endpoints, a  $\geq 20\%$  reduction from baseline in blood Phe level at any time of the iTD of SYN1934v1, and a  $\geq 20\%$  reduction from baseline in blood Phe level at any time in the DEP. The proportion of participants meeting these criteria will be summarized along with 95% confidence intervals.

These analyses will be performed on the DEP FAS.

### **8.5.2. Part 2: RWP**

The key secondary efficacy endpoints for the RWP are:

- Percent change from DEP baseline in blood Phe level at Week 4.
- Change from DEP baseline to Week 4 in blood Phe level
- Blood Phe level  $\leq 360$   $\mu\text{mol/L}$  at Week 4.

The proportion of participants meeting the key secondary endpoint, a blood Phe level  $\leq 360$   $\mu\text{mol/L}$  at Week 4, will be tested between the placebo and SYNB1934v1 dose groups using a Fisher's Exact test. The key secondary endpoint, change from DEP baseline to Week 4 in blood Phe level, will be analyzed using an MMRM analysis similar to the model described for the RWP primary efficacy analysis (Section 8.4), with the dependent variable being the change in blood Phe level from DEP baseline, and the DEP baseline blood Phe level as the baseline blood Phe level covariate. The key secondary endpoint, percent change from DEP baseline in blood Phe level at Week 4, will be analyzed using an MMRM analysis similar to the model described for the RWP primary efficacy analysis (Section 8.4), with the dependent variable being the percent change in blood Phe level from DEP baseline, and the DEP baseline blood Phe level as the baseline blood Phe level covariate.

These analyses will be performed on the responder RWP FAS.

## 8.6. Other Secondary Efficacy Endpoint Analyses

### 8.6.1. Part 1: DEP

The secondary efficacy endpoints for the DEP are:

- Blood Phe level  $\leq 360$   $\mu\text{mol/L}$  at any time of the iTD of SYNB1934v1
- Blood Phe level  $\leq 360$   $\mu\text{mol/L}$  at any time in the DEP.

For each of these 2 endpoints, the proportion of participants meeting the endpoint will be summarized along with [REDACTED]. These analyses will be performed on the DEP FAS.

### 8.6.2. Part 2: RWP

The additional secondary efficacy endpoints for the RWP are:

- $A \geq 20\%$  reduction from DEP baseline in blood Phe level at Week 4.

The proportion of participants achieving a  $\geq 20\%$  reduction in blood Phe level from baseline to Week 4 will be tested between the placebo and SYNB1934v1 dose groups using a Fisher's Exact test.

These analyses will be performed on the responder RWP FAS.

## 8.7. Exploratory Endpoint Analyses

The analysis methods for the exploratory endpoints will be presented in the SAP.

## 8.8. Missing Data

The primary efficacy endpoint analyses for the DEP and RWP will be an observed-case analysis. Missing data will not be imputed for the primary efficacy analyses.

For the following key secondary efficacy analyses, an observed-case analysis will also be applied:

- DEP Part 1: Change from baseline in blood Phe level at last measurement of the iTD of SYN1934v1
- RWP Part 2: Change from DEP baseline to Week 4 in blood Phe level
- RWP Part 2: Percent change from DEP baseline in blood Phe level at Week 4

For the following dichotomous key secondary efficacy analyses, an observed-case approach is being applied such that if a participant is missing the data needed to determine the endpoint, they will be considered as not having met the endpoint.

- DEP Part 1:  $A \geq 20\%$  reduction from baseline in blood Phe level at any time of the iTD of SYN1934v1
- DEP Part 1:  $A \geq 20\%$  reduction from baseline in blood Phe level at any time in the DEP
- RWP Part 2: Blood Phe level  $\leq 360$   $\mu\text{mol/L}$  at Week 4.

Sensitivity analyses considering different methods of handling missing data for the primary and key secondary efficacy endpoints will be specified in the SAP. Additional details on the handling of missing data will be provided in the SAP.

## 8.9. Multiplicity

The overall Type I error rate for the DEP will be controlled at the 2-sided 0.05 level for the primary endpoint. If the DEP primary endpoint analysis is significant at the 2-sided 0.05 level the key secondary endpoint, change from baseline in blood Phe level at last measurement of the iTD of SYN1934v1, will be tested at the 2-sided 0.05 level. Note that the 2 dichotomous DEP key secondary endpoints; a  $\geq 20\%$  reduction from baseline in blood Phe level at any time of the iTD of SYN1934v1, and a  $\geq 20\%$  reduction from baseline in blood Phe level at any time in the DEP - do not have an associated inferential test.

The overall Type I error rate for the RWP will also be controlled at the 2-sided 0.05 level for the primary endpoint (i.e., DEP, and RWP, will each have a 2-sided Type I error rate of 0.05). The control of multiplicity at 0.05 within each study part is consistent with this study having 3 parts, with each study part having a distinct set of objectives, endpoints, and analysis populations.

For the RWP, the 3 key secondary endpoints will be tested at the 2-sided 0.05 level using a fixed sequential testing methodology in this order:

- 1) Percent change from DEP baseline to Week 4 in blood Phe level
- 2) Change from DEP baseline to Week 4 in blood Phe level
- 3) Blood Phe level  $\leq 360$   $\mu\text{mol/mL}$  at Week 4

These key secondary endpoints will be tested following this prespecified order only if the RWP primary efficacy endpoint null hypothesis is rejected.

## 8.10. Safety Analysis

Safety will be evaluated by scheduled monitoring of AEs, vital signs, and clinical laboratory measurements. Safety parameters will be summarized descriptively by the treatment regimen (dose and frequency) that the participant was on at the time of the safety measurement.

By-participant listings of all measurements and parameters will be presented in tabular format, including absolute values and changes from baseline (if applicable), by dose cohort and study day.

Adverse events will be coded using the *Medical Dictionary for Regulatory Activities*, and severity of AEs and laboratory abnormalities will be graded using the National Cancer Institute CTCAE, v5.0, with certain exceptions as listed in [Table 7](#). Adverse events will be tabulated by study period, treatment group, system organ class, and preferred term. Incidence tables of participants with AEs will be presented for all AEs by maximum severity, AESIs, SAEs, AEs assessed as related to IMP, and AEs resulting in discontinuation of study dosing.

For the DEP, safety analyses will be performed on the DEP SAS. For the RWP and OLE study parts, safety analyses will be performed on the corresponding SAS, with results being presented for the responder and nonresponder populations as well as overall population.

## 8.11. Randomization and Blinding

In the RWP, participants will be randomized in a 1:1 ratio to receive either SYN1934v1 or matching placebo, stratified on screening Phe level (361 to 720  $\mu\text{mol/L}$ , or  $> 720 \mu\text{mol/L}$ ). Participants, investigators, and the sponsor will be blinded to randomized IMP assignment during the RWP. In the case of an emergency where information regarding treatment assignment would impact the care provided to a participant during the RWP of the study, the investigator will have immediate access to unblind the treatment code in the interactive response system (IXRS). The instructions for unblinding a subject in the IXRS can be found in the IXRS User Guide. In the event unblinding is necessary, the investigator is strongly encouraged to contact the medical monitor to discuss the situation and the subjects medical status prior to unblinding. It is mandatory that any personnel involved in the unblinding or who have access to the unblinded treatment assignment maintain the confidentiality of the information.

During the DEP and RWP, blood Phe levels will be blinded to the participant, investigator and sponsor. During the DEP and RWP, the investigator will receive an email alert from the central laboratory if a blood Phe is  $> 1.5 \times$  the DEP baseline, if Phe is  $< 30 \mu\text{mol/L}$ , or if Tyr is  $< 20 \mu\text{mol/L}$ . After the receipt of one of these trigger values, the investigator should arrange for a retest of Phe and Tyr. If the trigger value is confirmed to be out of range, the individual participant will be discontinued from the study.

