**Removal of Individual Participants from Investigational Medicinal Product and Withdrawal of Consent**

Reasons for discontinuation of investigational medicinal product (IMP; i.e., SYNBI934v1 or placebo) may include the following:

- The participant withdraws consent.
- The investigator or sponsor notes a significant noncompliance with protocol procedures.
- The participant develops an intolerable toxicity including but not limited to a Grade 3 or more severe adverse event or serious adverse event (SAE) assessed as related to IMP by the investigator.
- The investigator determines that the participant must discontinue further study dosing for medical reasons (including pregnancy).
- The participant has low levels of Phe ( $< 30 \mu\text{mol/L}$ ) or Tyr ( $< 20 \mu\text{mol/L}$ ) or has profound elevations in Phe ( $> 1.5 \times$  the DEP baseline value during DEP and RWP and  $> 2200 \mu\text{M}$  during OLE).

If possible, the investigator will confer with the sponsor or medical monitor before discontinuing dosing. Participants who discontinue from IMP in RWP will be encouraged to remain on study and complete assessments (particularly safety assessments) through the remainder of RWP of the study. Participants who discontinue from DEP and OLE will be asked to have an early termination visit 30 days after the last dose of IMP.

Participants may withdraw their consent at any time for any reason without prejudice to their future medical care by the physician or at the institution. If a participant withdraws consent, the date and stated reason for consent withdrawal should be documented. Participant data collected up to the date of consent withdrawal will be included in the analyses.

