### 3.5. Study Discontinuation for Individual Participants

Reasons for discontinuation of IMP may include the following:

- The participant withdraws consent.
- The investigator or sponsor notes a significant noncompliance with protocol procedures (e.g., use of a prohibited concomitant medication).
- The participant develops an intolerable toxicity including but not limited to a Grade 3 or more severe AE or SAE assessed as related to IMP by the investigator.
- The investigator determines that the participant must discontinue further study dosing for medical reasons (including pregnancy).
- The participant has low levels of Phe ( $< 30 \mu\text{mol/L}$ ) or Tyr ( $< 20 \mu\text{mol/L}$ ) or has profound elevations in Phe ( $> 1.5 \times$  the DEP baseline value during DEP and RWP and  $> 2200 \mu\text{M}$  during OLE).

If possible, the investigator will confer with the sponsor or medical monitor before discontinuing dosing. Participants who discontinue from IMP in RWP will be encouraged to remain on study

and complete assessments (particularly safety assessments) through the remainder of RWP. Participants who discontinue from DEP and OLE will be asked to have an early termination visit 30 days after the last dose of IMP (see Section 5.6).

Participants may withdraw their consent at any time for any reason without prejudice to their future medical care by the physician or at the institution. If a participant withdraws consent, the date and stated reason for consent withdrawal should be documented. Participant data collected up to the date of consent withdrawal will be included in the analyses.

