## **5.6. Early Termination Assessments**

Participants who discontinue prematurely during the DEP or OLE will complete an early termination visit no sooner than 30 days after the last dose of IMP, as detailed in [Table 6](#).

Participants who discontinue prematurely during the RWP will complete RWP visits as scheduled prior to the early termination visit and will also complete an early termination assessment no sooner than 30 days after the last dose of IMP. Participants will be discharged from the study after this visit.

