2.5.2 Part 2: Primary and Key Secondary Efficacy Objectives Estimands

The estimands corresponding to the Part 2 RWP primary and key secondary objectives and endpoints are described in [Table 6](#) and [Table 7](#), respectively.

Table 6: Estimand for the RWP Part 2 Primary Objective

Objective	To evaluate efficacy of SYNB1934v1 versus placebo in the responder population
A. Population	The population is the RWP responder full analysis set (defined in Section 3.5) characterized by the inclusion/exclusion criteria provided in Section 4.2 of the study protocol.
B. Variable	Continuous variable: Change from RWP baseline to Week 4 in blood Phe level

C. Intercurrent events	
• Treatment discontinuation: consistent with a treatment-policy strategy, treatment discontinuation will not be considered (i.e., all observed data will be used regardless of treatment discontinuation).• Antibiotic use: consistent with a treatment-policy strategy, antibiotic use will not be considered (i.e., all observed data will be used regardless of antibiotic use).• Prohibited medication use: consistent with a treatment-policy strategy, prohibited medication use will not be considered (i.e., all observed data will be used regardless of prohibited medication use).
D. Population-level summary	The population-level summary is the least-squares means and difference in the change from baseline to Week 4 in blood Phe levels between the SYNB1934v1 and placebo treatment groups. An MMRM using an observed case approach is being applied. The post-baseline blood Phe levels at Weeks 1, 3, and 4 will be used. The MMRM model is described in Section 3.14.2.1 .

MMRM = mixed model with repeated measures; Phe = phenylalanine; RWP = randomized withdrawal period.

Table 7: Estimands for the RWP Part 2 Key Secondary Objectives

Objective	To evaluate the efficacy of SYNB1934v1 versus placebo in the responder population with regard to the percent change from DEP baseline in blood Phe level
A. Population	The population is the RWP responder full analysis set (defined in Section 3.5) characterized by the inclusion/exclusion criteria provided in Section 4.2 of the study protocol.
B. Variable	Continuous variable: Percent change from DEP baseline to Week 4 in blood Phe level.

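### A confirmed Phe or Tyr trigger ends study participation in two sections but only study treatment elsewhere, so it is unclear whether the later RWP Phe values are collected

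*Protocol*

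**What the plan says.** Three instructions apply to the same event in the RWP.

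- **Leave the study.** Protocol 8.11 has the central laboratory alert the investigator to Phe above 1.5 times DEP baseline, Phe below 30 µmol/L or Tyr below 20 µmol/L, followed by a retest. If the retest confirms the value, "the individual participant will be discontinued from the study". SAP 2.2.2 repeats this sentence.
- **Stop IMP, possibly, and be encouraged to stay.** Protocol 3.5 opens its list with "Reasons for discontinuation of IMP may include the following". One item begins "The participant has low levels of Phe" and goes on to the same Tyr and high-Phe limits. The section then says: "Participants who discontinue from IMP in RWP will be encouraged to remain on study". The synopsis has the same list and the same request: "Participants who discontinue from IMP in RWP will be encouraged to remain on study and complete assessments".
- **Finish the visits.** Protocol 5.6 says: "Participants who discontinue prematurely during the RWP will complete RWP visits as scheduled", with the early termination visit afterwards. Table 5 footnote c agrees.

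For the RWP primary endpoint, Protocol 7.2 (Table 10) and SAP 2.5.2 (Table 6) handle treatment discontinuation by treatment policy. The SAP adds that "all observed data will be used regardless of treatment discontinuation". The primary analysis is an observed-case MMRM on Weeks 1, 3 and 4 without imputation (Protocol 8.8, SAP 3.14.2.1). For Week 4 Phe at or below 360 µmol/L, a missing value counts as not met (Protocol 8.8, SAP 3.14.2.4). SAP 3.20, which lists departures from the protocol, does not mention the trigger.

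**The concern.** A treatment-policy estimand needs the outcome measured after treatment stops. A site that follows 8.11 to the letter could end visits at the confirmed trigger, and values that are never drawn cannot be used.

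The loss would not be random. The trigger is defined on the outcome variable itself. A high-Phe trigger is more likely in a participant withdrawn to placebo; a low Phe or Tyr trigger is more plausible on active treatment. SAP 3.6.1 lists low Phe or Tyr, or profoundly elevated Phe, among the reasons for not completing a study part, so the event is expected to appear in the disposition tables.

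At stake are the Week 3 and Week 4 values after a trigger, and the analyses that depend on Week 4 alone.

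**Working it through.** **Which values are at risk.** RWP Phe is drawn at Weeks 1, 3 and 4.

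| Confirmed trigger at | Kept | Lost if visits stop |
|---|---|---|
| Week 1 | Week 1 | Weeks 3 and 4 |
| Week 3 | Weeks 1 and 3 | Week 4 |
| Week 4 | all three | no RWP value |

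The value that sets off the trigger is always in the data.

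**Inputs from the documents.** The synopsis gives a treatment difference of -245 µmol/L, SD of change 247 µmol/L, 1:1 allocation, 5% RWP dropout and two-sided 0.05. The RWP sample size and power are redacted, so there is no stated figure to reproduce.

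**Assumptions not in the documents.** Mean DEP baseline 600, 850 or 1100 µmol/L (CV 35%); visit-level SD 150, 200 or 247 µmol/L at the mean baseline, scaled with each participant's baseline; between-visit correlation 0.3 or 0.6; a 30% reduction held on active; placebo returning to DEP baseline; retest error 0.3 of the visit SD. Only the high-Phe trigger was modelled.

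**Method.** There were 400,000 simulated participants per scenario. A participant left after Phe and its retest both exceeded 1.5 times DEP baseline at Week 1 or Week 3. Three Week 4 differences were compared:

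1. Full data: regression of Week 4 change on treatment and RWP baseline.
2. Likelihood estimate equivalent to the MMRM under monotone dropout. With d1 the Week 1 treatment effect: d3 = b3(treatment) + b3(Week 1) × d1; d4 = b4(treatment) + b4(Week 1) × d1 + b4(Week 3) × d3. Each regression uses those still in the study.
3. ANCOVA on observed Week 4 values only.

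Selected results (differences in µmol/L; all are active minus placebo):

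| Baseline / SD / correlation | Week 4 lost, placebo vs active | Full | MMRM | ANCOVA |
|---|---|---|---|---|
| 600 / 247 / 0.3 | 16.6% vs 3.9% | -178.5 | -184.6 | -161.4 |
| 600 / 247 / 0.6 | 15.1% vs 3.6% | -181.6 | -185.0 | -151.6 |
| 600 / 200 / 0.3 | 9.9% vs 1.2% | -181.2 | -184.9 | -170.3 |
| 850 / 247 / 0.3 | 6.5% vs 0.4% | -255.4 | -259.4 | -245.7 |
| 850 / 200 / 0.6 | 2.5% vs 0.0% | -255.2 | -256.0 | -247.9 |
| 1100 / 200 / 0.6 | 0.4% vs 0.0% | -328.9 | -329.1 | -327.4 |

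- Largest MMRM shift: 184.6 - 178.5 = 6.1, or 6.1/178.5 = 3.4%, away from the null.
- Largest ANCOVA shrinkage: 181.6 - 151.6 = 30.0, or 30.0/181.6 = 16.5%.
- The scenarios nearest the planning values are those at mean baseline 850 and visit SD 200. Their difference is about -255, and their placebo residual SD of change is about 240. There the ANCOVA shrinks by 1.5% to 2.8% (3.8/253.6 and 7.3/255.2) and the MMRM moves by less than 1%.

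**Second check.** This used the plan's 245 and 247 directly, fixed DEP baselines of 600, 800 and 1000, correlations 0.3 and 0.6, with and without a retest (12 scenarios). Week 4 was lost for up to about 20% of placebo and under 3% of active. The likelihood estimate stayed within 0.5 µmol/L of full data throughout. The comparison restricted to observed Week 4 values shrank by about 2% to 17%.

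**Power, for context only.** At difference 245 and SD 247, a t-test needs 23 per arm for 90% power (90.8% attained). Losing 1, 3 or 5 placebo participants outright gives 90.2%, 88.6% or 86.7%.

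**Endpoint of Phe at or below 360 µmol/L.** No simulation is needed. Suppose a participant has confirmed Phe below 30 at Week 1 or 3, leaves, and has no Week 4 value. Missing counts as not met, so this person enters the Fisher test as a failure on an endpoint met by a wide margin when last seen. No longitudinal model enters that test to use the earlier value. The endpoint is in the alpha-controlled sequence (Protocol 8.9, SAP 3.14.2.6). The documents give no rate for such events.

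**The case against.** The strongest defence is that the visits continue anyway. Protocol 5.6 and Table 5 footnote c cover anyone who discontinues early in the RWP, not only those who stop IMP, and discharge comes only after the early termination visit. Section 3.5 carries study discontinuation in its heading while its list concerns IMP, so the protocol uses the two terms loosely. On that reading 8.11 need not end any visit. This stands in part: the loss is conditional and is not the plan's settled outcome. But 8.11 is the section that says what follows a confirmed trigger, and the SAP repeats it, so a site could reasonably stop visits.

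A reader might infer that losing high placebo values pulls the placebo Week 4 mean down and so shrinks the primary effect. The documents do not support that. The primary analysis is an MMRM that keeps the triggering Week 1 or Week 3 value, so removal depends largely on observed data. It would likewise be wrong to size the bias by cutting off the placebo Week 4 distribution at 1.5 times DEP baseline, because a Week 4 value that triggers has already been drawn.

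It is also fair that the simulated losses may be too high. The primary population is selected for a fall of at least 20% from DEP baseline, and regression to the mean could leave placebo below that baseline, which would make the high trigger rarer.

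**Conclusion.** The contradiction is real and unresolved. If 8.11 and SAP 2.2.2 are followed literally, RWP Phe values after a confirmed Week 1 or Week 3 trigger are not collected, although the RWP estimands call for them.

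The expected effect on the primary MMRM is small: at most about 6 µmol/L (about 3%) in the scenarios tried, slightly away from the null. Two analyses are more exposed:

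- The Week 4 observed-case ANCOVA (SAP 3.14.2.3) shrank toward the null by 0 to 17%, and by less than 3% in the scenarios nearest the planning values.
- The Week 4 endpoint of Phe at or below 360 µmol/L can score a very low Phe value as a failure.

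The planned MNAR analysis (SAP 3.18.2.2) does not cover the gap. It imputes missing active-arm values from the placebo distribution, so it does not stress informative loss on placebo.

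The sizes rest on assumed baselines, visit SDs and correlations, on placebo returning to DEP baseline, and on a retest whose error is independent of later visits. If the retest carried extra information about later values and stayed outside the model, the MMRM would be somewhat less protected. The textual conflict and its remedy do not depend on these figures.

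**What to change.** Reconcile Protocol 8.11 and SAP 2.2.2 with the synopsis, Protocol 3.5, Protocol 5.6 and Table 5 footnote c, so that all say the same thing about whether a confirmed trigger ends IMP or study participation. Which clinical rule applies is for the sponsor and investigators; no threshold or stopping rule is proposed here.

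Whatever treatment-stopping rule is kept, add one sentence to both documents: the remaining scheduled RWP Phe assessments, Week 4 included, are still collected unless the participant withdraws consent. Record the clarification in SAP 3.20.

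The cost is wording. The visits are already in the schedule of events, and SAP 3.20 already expects a further protocol amendment.
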